Study Day 4: Approximately 72 hours after the time of study drug administration on Study Day 1, participants will undergo an individual, virtual (via web meeting, phone, etc.) integration session, and be assessed for adverse events including mental health issues as well as for changes in concomitant medications and clinician rating scales and patient QoL/PRO instruments will be completed.

Study Day 8: One week following Study Day 1, participants will return to the study site to undergo a physical exam, have vital signs measured, and share any changes in concomitant medications as well to be assessed for adverse events. Participants also will be administered clinical rating scales and complete their QoL and PRO instruments. Participants will provide blood and saliva samples for clinical laboratory evaluations and for epigenetic testing.

Study Day 30: Unless discontinued from participation earlier, at one month following Study Day 1, participants will return to the study site for an End-of-Treatment (EOT) visit. Patients that prematurely discontinued participation on, or after being treated on Study Day 1 will be encouraged to return to the study site for the EoT visit as soon as possible and need not wait till Study Day 30).

At the EoT visit, participants will be assessed for adverse events and changes in concomitant medications, have vital signs measured, provide urine samples for drug and alcohol screening and blood samples for clinical laboratory evaluations as well as undergo clinical rating scale assessments and complete their QoL and PRO instruments.

Study Day 90: Three months following Study Day 1, participants will return to the research study center for the Long-Term Follow-up (LTFU) visit. At the LTFU visit, participants will be assessed for adverse events deemed to be 'possibly' or 'probably' related to the single dose of the investigational product administered on Study Day 1 and/or to assess any AEs that were not resolved by the EoT visit.

Participants also will have vital signs measured, provide urine samples for drug and alcohol testing as well as undergo and/or complete rating scale assessments and QoL and PRO

instruments, respectively.

Participants also will return the health tracking wearable device and the data collected will be downloaded to the trial database.

Upon completion of the 3-month LTFU visit and after the study site staff obtain all outstanding data, participants will have completed the study.

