4.2. Premature Discontinuation

Participants can elect to prematurely discontinue their involvement in this trial at any time and for any reason (see Section 6.3 for more detailed information regarding a participant's rights and responsibilities). If a decision to prematurely discontinue participation is made, the Investigator (or designee) may ask the individual to continue to be followed for safety and indicate that they will not have to undergo any other tests, examinations or procedures. However, the participant will not be coerced into continuing to be involved in the trial, even in a less demanding manner.

Otherwise, the participant can terminate their involvement in the trial, without prejudice, and not affect their continued medical care.

Participants also may be prematurely discontinued from the trial by the Investigator if it is determined that continued involvement could adversely affect their health and/or wellbeing. Other reasons for premature discontinuation include adverse effects, a participant's lack of adherence to the requirements of the protocol or other issues that, in the opinion of the Investigator could confound the assessments of safety (and/or preliminary efficacy) of the investigational product.

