5.3. Withdrawal of Participants

Participants can withdraw their consent to continue participating in this trial at any time, without prejudice and with no impact on their subsequent medical care.

The Investigator can withdraw a participant from continued participation in the trial if, in his or her clinical judgment, it is in the best interest of the participant or if the participant cannot

CONFIDENTIAL

comply with the experimental procedures and related visits that are critical to assess the safety of the investigational product.

Regardless of the reason, any withdrawal (or discussion about withdrawing) from continued participation in the trial will be recorded in the participant's personal medical record (i.e., source document). If a patient prematurely discontinues participation in the trial, the date of and reason(s) for discontinuation will be recorded in the electronic case report form (eCRF).

Among the reasons that may require participants to prematurely discontinue participation is that they may not be able to comply with one or more eligibility criteria such as the prohibited use of certain concomitant medications. If the Investigator withdraws a participant from the trial, the reason(s) for the decision will be explained to the participant. If the Investigator feels it is needed, the participant may be referred for continued PTSD (and/or other medically necessary) care.

As necessary, participants that are withdrawn due to AEs will continue to be clinically monitored until the event resolves, unless the participant refuses to do so.

Whenever possible, the Investigator or another member of the research study team will ask any participant that chooses to withdraw or is withdrawn by the Investigator to return to the study site as soon as convenient to undergo the protocol's mandated tests, examinations, procedures and assessments that are required for the Day 30, EoT visit. Nonetheless, the decision to return to the study site and undergo some or all of the activities required at the EoT visit rests entirely with the participant. As noted in Section 5.2, the patient should not be coerced into continuing to be involved in the trial, even in a less demanding manner.

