7.1.8 Study Day 30 / End-of-Treatment (EoT) Assessments

One month after Study Day 1, participants will return to the study center on Study Day 30.

Likewise, any participant that self-administered study drug on Study Day 1, but that prematurely discontinues participation in the trial, for any reason, should be encouraged to undergo an End-of-Treatment visit. If the participant was discontinued prior to the Study Day 8 visit, additional tests and examinations will be performed at the EoT visit. For discontinued participants, the Study Day 8 visit should be scheduled as soon as practical to ensure collection of needed safety, and preliminary efficacy data.

- As noted in Section 8.1.1, participants that are prematurely discontinued before Study Day 3, for any reason except due to an adverse event, may be replaced, at the discretion of the Investigator.

The protocol-mandated tests, examinations, assessments and procedures to be performed during the Study Day 30 / EoT visit are presented below:

- Inquire about any changes in the participant's health in a non-suggestive manner and review concomitant medications/therapies (including psychotherapy and healthcare utilization).

CONFIDENTIAL

- Perform a brief physical exam and obtain weight (only if Study Day 8 visit was not completed).
- Obtain vital sign measurements.
- Obtain blood samples for clinical laboratory evaluations.
- Obtain saliva sample for epigenetic analysis (only if Study Day 8 visit was not completed).
- Obtain urine samples for:
 - Qualitative rapid urine drug screen.
 - Qualitative urine ethyl glucuronide (EtG) test to assess alcohol consumption.
- Review participant's use of health tracking wearable device and collect the device and download the data to the trial database (if the participant prematurely discontinued participation in the trial and will not be undergoing the 3-month Long Term Follow-up visit).
- Administer and/or have the participant complete the following clinician rating scales and participant QoL and PRO instruments, respectively:
 - GAD-7
 - PHQ-9
 - BPI
 - NIH HEALS
 - C-SSRS
 - SDS
 - AUDIT (only if the participant was prematurely discontinued)
 - DUDIT (only if the participant was prematurely discontinued)

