If the participant prematurely discontinues from the trial, this will be their last study visit, unless there is an ongoing adverse event that will continue to be monitored until resolution or until the Investigator and Medical Monitor determine that no additional follow-up is medically necessary.

Otherwise, the participant will return to the study site for the final 3-month, LTFU, visit.

7.1.9 3-Month Long-Term Follow-up (LTFU) Visit

Approximately three months (i.e., 90 days) after Study Day 1, participants will return for the final, 3-month, Long-Term Follow-up (LTFU) visit. At this visit, a number of protocol-mandated tests, examinations, assessments and procedures will be done as described below.

- Inquire about any changes in the participant's health in a non-suggestive manner; however, any changes noted will not be considered adverse events unless they either were noted prior to the Study Day 30 / EoT visit and/or are considered to be 'possibly' or 'probably' related to study drug administration.
- Review concomitant medications/therapies (including psychotherapy and healthcare utilization).
- Perform a brief physical exam and obtain weight (only if Study Day 8 visit was not completed).

CONFIDENTIAL

- Obtain vital sign measurements.
- Obtain urine samples for:
 - Qualitative rapid urine drug screen.
 - Qualitative urine ethyl glucuronide (EtG) test to assess alcohol consumption.
- Review participant's use of health tracking wearable device and collect the device and download the data to the trial database.
- Administer and/or have the participant complete the following clinician rating scales and participant QoL and PRO instruments, respectively:
 - GAD-7
 - PHQ-9
 - BPI
 - NIH HEALS
 - C-SSRS
 - AUDIT
 - DUDIT

Upon completion of the 3-month, long-term follow-up visit and after the study site staff obtain all outstanding data, participants will have completed the study, except if there is an ongoing adverse event that the Investigator and/or Medical Monitor believe warrants continued monitoring until resolution or until it is determined that no additional follow-up is medically necessary.

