9.4. Criteria for Termination or Suspension of the Study

The study will be fully enrolled and completed as planned unless one or more of the following criteria are satisfied that require temporary suspension of the study.

- New information regarding the safety or efficacy of the study drug indicates a significant change in the known risk/benefit profile for the drug, such that the risk is no longer acceptable for subjects participating in the study.
- Significant violation of Good Clinical Practice (GCP) that compromises the ability to achieve the primary study objectives or compromises subject safety.
- Study-specific criteria for suspension of the study:
 - The study will be paused if:
 - One participant experiences any of the following during the treatment phase of the trial starting at the time of study drug administration and through Study Day 30/ EoT, even if the participant prematurely discontinued further involvement in the trial:
 - A CTCAE Grade 3 – 5 toxicity which is possibly or probably related to study treatment,
 - A suicide attempt,
 - A marked prolongation of QT interval (i.e., $QT \geq 450$ msec) over a series of 3 ECGs performed within 5-6 minutes,
 - A serious episode of psychosis as determined by the Investigator that requires immediate medical attention,
 - A severe, non-serious, AE possibly related to study treatment,
 - Two participants experience: One or more serious AE's possibly or probably related to study treatment.

The study might also be terminated by the sponsor for the following reasons:

- Slow patient enrollment,
- Data collected lacking quality,
- Poor adherence to protocol,
- Other findings that could lead to the study not meeting its objectives.

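### After an early End-of-Treatment visit, dosed participants who leave have no scheduled safety contact to Day 30 or Day 90, although the pausing rule in Section 9.4 still covers them

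*Protocol*

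**What the plan says.** All study drug is given on Day 1, so leaving afterwards ends observation, not exposure. Five sections of the protocol govern what happens next.

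- **Section 4.1:** those who discontinue after dosing "will be encouraged to return to the study site for the EoT visit as soon as possible and need not wait till Study Day 30".
- **Section 7.1.8:** "If the participant prematurely discontinues from the trial, this will be their last study visit, unless there is an ongoing adverse event". The same section also says "For discontinued participants, the Study Day 8 visit should be scheduled as soon as practical", in a paragraph that is otherwise about the EoT visit.
- **Section 4.2:** the Investigator "may ask the individual to continue to be followed for safety", without further tests. No schedule, content or end date is given.
- **Section 5.3:** leavers are asked back for the EoT assessments, with the decision left to them. In addition, "participants that are withdrawn due to AEs will continue to be clinically monitored until the event resolves", unless the participant refuses.
- **Section 9.4:** the study is paused if "One participant experiences any of the following during the treatment phase of the trial". The list includes a related Grade 3 to 5 toxicity, a suicide attempt and a serious psychotic episode. The window runs from dosing "through Study Day 30/ EoT, even if the participant prematurely discontinued further involvement in the trial".

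Section 10.3 ties AE collection to the participant's involvement in the trial, and says that psychiatric AEs are collected throughout the study. Section 9.5 provides a hotline for psychological crises.

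**The concern.** Safety is the primary objective, and one qualifying event is enough to pause the trial. Section 9.4 states that leavers remain covered, but the visit schedule does not include any contact that would ask them about a new event once the early EoT is done.

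The protocol itself foresees such leavers. Section 7.1.1 allows replacement of treated participants who discontinue by Day 3 for reasons other than an AE. Under Section 7.1.4, a participant whose anxiety, depression or suicidal ideation is above baseline after dosing stays overnight. The morning evaluation then determines whether they continue, and they go home only once symptoms are back to baseline or lower. If that evaluation ends participation, the event may already count as resolved, so the provisions for ongoing AEs need not apply. A participant removed by the Investigator has not necessarily refused follow-up either.

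**Working it through.** The protocol has no figure of its own to reproduce on this point: Section 12.2 gives up to 24 treated participants without a calculation, and no dropout rate after dosing is stated. The check is therefore mainly of the text, followed by an illustration.

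**Step 1. Does any route schedule a contact that could find a new event after an early EoT?**

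- Section 4.2 follow-up: optional and unscheduled.
- Section 5.3 monitoring and the exception in 7.1.8: only events already known.
- Section 9.5 hotline: depends on the participant calling.
- Section 10.3, psychiatric AEs throughout the study: states an intent but names no contact for someone past their last visit.
- The 3-month visit: footnote 13 to Table 1 and the wearable-device item in 7.1.8 leave open that some leavers attend it, but 7.1.8 says EoT is normally the last visit.

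None of them schedules one.

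**Step 2. Where does the 9.4 window end for a leaver?** The phrase in 9.4 treats Day 30 and EoT as one date, and 4.1 separates them. If the window ends at Day 30, no scheduled contact covers its last part. If it ends at the actual EoT, the window shortens for exactly those who left, and the clause extending the rule to them adds little. Either way the sections need reconciling.

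**Step 3. Days without scheduled contact for one leaver.** Day 1 to Day 30 is 29 days. Days left after EoT on day d = 30 − d.

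| EoT on | Days left | Share of 29 |
|---|---|---|
| Day 4 | 26 | 90% |
| Day 5 | 25 | 86% |
| Day 8 | 22 | 76% |
| Day 15 | 15 | 52% |

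To Day 90 (89 days), an EoT on Day 5 leaves 90 − 5 = 85 days.

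**Step 4. Effect on the trial under assumed dropout.** Assume that k of 24 participants leave with EoT on Day 4. Planned person-days to Day 30 are 24 × 29 = 696. As a worst case, treat every event in these leavers as missed, so that n = 24 − k. The upper limit is the one-sided 95% limit for zero observed events, 1 − 0.05^(1/n). The chance of seeing at least one trigger event is 1 − 0.95^n, at an assumed 5% event rate.

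| k | Person-days without contact | Upper limit | Chance of seeing a trigger |
|---|---|---|---|
| 0 | 0 | 11.7% | 0.708 |
| 2 | 52 of 696 (7.5%) | 12.7% | 0.676 |
| 4 | 104 of 696 (14.9%) | 13.9% | 0.642 |

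The values of k, the EoT day and the event rate are all assumptions.

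**The case against.** The best defence is that leavers are not abandoned. The text speaks of a last study visit, not a last contact. Known AEs are followed, the Investigator may ask for continued safety follow-up, and there is a hotline. An event learned of by any of these routes would count under 9.4. A reader might infer that nothing can reach the pausing rule after an early EoT, or that the rule cannot fire on a leaver. The documents do not support that. What stands is narrower: no scheduled contact looks for a new event.

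A second objection is that completers also have no scheduled contact between Day 8 and Day 30, so prompt detection in those weeks relies on unscheduled reports for everyone. That is correct. Completers are, however, asked at Day 30 about the whole interval. A leaver with an early EoT is not, and may miss the Day 8 visit as well.

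Third, 4.2 and 5.3 can be read together, as a request for the EoT assessments with a lesser option for those unwilling. That is fair, and I do not count them as contradictory. The Day 8 wording in 7.1.8 is a small slip.

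Finally, a reader might infer that leavers will be counted as event-free after the early visit, or that their early scale scores will be reported as Day 30 results. The protocol states neither. Visit mapping and incomplete follow-up may be settled in the SAP, which is not at hand. The SAP cannot, however, recover events that nobody asked about.

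**Conclusion.** The gap is real and concerns the primary objective. For a dosed participant who leaves early without an ongoing AE, learning of new events up to Day 30 and Day 90 depends on optional or participant-initiated contact, while 9.4 says the pausing rule still applies, to an end date that can be read two ways. This is an ambiguity between sections combined with a missing contact, rather than a flat contradiction.

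For one leaver with EoT on Day 5, the share of days to Day 30 without scheduled contact is 86%. That figure should not be read as a loss for the whole trial. In the assumed worst cases of 2 or 4 leavers among 24, the effect on the upper limit and on the chance of seeing a trigger is modest. The true size is unknown. The point matters because a single event triggers a pause, and because observation not made at the time may not be recoverable.

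**What to change.** - In 4.2, 5.3 and 7.1.8, separate stopping study procedures from stopping safety follow-up.
- For dosed leavers who do not refuse, schedule a remote AE and C-SSRS contact, in the format already used on Day 4, at the nominal Day 30 and Day 90 times.
- Keep the prompt early visit, but record it as an early-termination visit by its actual study day.
- Reconcile 4.1, 7.1.8, 9.4 and 10.3 so that 9.4 gives one unambiguous end of the window for discontinued participants. Which end date to use is for the sponsor to decide.
- Reconcile the Day 8 wording in 7.1.8 with the EoT visit that it appears to mean.

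The cost is amendment wording and two short calls per leaver, some of which will be declined. The calls cannot supply the ECGs that the QT criterion in 9.4 needs, so they narrow the gap without closing it.

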4.2. Premature Discontinuation

Participants can elect to prematurely discontinue their involvement in this trial at any time and for any reason (see Section 6.3 for more detailed information regarding a participant's rights and responsibilities). If a decision to prematurely discontinue participation is made, the Investigator (or designee) may ask the individual to continue to be followed for safety and indicate that they will not have to undergo any other tests, examinations or procedures. However, the participant will not be coerced into continuing to be involved in the trial, even in a less demanding manner.

Otherwise, the participant can terminate their involvement in the trial, without prejudice, and not affect their continued medical care.

Participants also may be prematurely discontinued from the trial by the Investigator if it is determined that continued involvement could adversely affect their health and/or wellbeing. Other reasons for premature discontinuation include adverse effects, a participant's lack of adherence to the requirements of the protocol or other issues that, in the opinion of the Investigator could confound the assessments of safety (and/or preliminary efficacy) of the investigational product.

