5.1.2 Exclusion Criteria

1. Currently uncontrolled hypertension. ($>140/90$ at Screening and $>145/95$ on Study Day 1).
2. History of recent seizure (within 3 months of Study Day 1).
3. History of stroke or transient ischemic attacks.
4. Preexisting history of valvulopathy or pulmonary hypertension.
5. A marked prolongation of QT interval (i.e., $QT \geq 450$ msec) over a series of 3 ECGs performed within 5-6 minutes.

CONFIDENTIAL

6. Currently uncontrolled diabetes ($HbA1c > 8.0\%$).
7. Potential for adverse drug-drug interactions such as the use of centrally-acting serotonergic agents within 24 hours prior to and for 72 hours following study drug administration on Study Day 1.
8. Significant suicide risk defined by (1) suicidal ideation as endorsed on items 4 or 5 on the Columbia Suicidal Severity Rating Scale (C-SSRS) within the last 6 months, at Screening, or at Baseline (Visit 1), or; (2) suicidal behaviors within the last 12 months as assessed by C-SSRS.
9. Patients with severe anxiety and depression measured as following: Participants with scores of 15 & above on Generalized Anxiety Disorder-7 (GAD-7) scale, and/or with scores of 20 & above on Patient Health Questionnaire-9 (PHQ -9).
10. Are pregnant or nursing or are women of childbearing potential who are not practicing a highly effective means of birth control.
11. Have any allergies or contraindication to psilocybin mushrooms.
12. Current users of psilocybin, LSD, DMT, Ayahuasca, Peyote, mescaline, and ketamine over the past 30 days will not qualify for the study unless the use of these agents is stopped for 30 days prior to Study Day 1 and the participant agrees to not use these (or similar) agents for 30 days after Study Day 1.
13. Are not able to attend face-to-face visits at the study site or plan to move out of the area prior to the 3-month LTFU visit.
14. Have any current problem that, in the opinion of the Investigator or Medical Monitor, might interfere with an individual's participation in the study or confound the assessment of safety and/or efficacy of the study drug.

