6.5. Dose and Administration

6.5.1 Dose

For the visit, study participants will self-administer a total dose of 30 mg ($\pm 10\%$) of psilocybin, derived from whole, dried, ground organic psilocybin mushrooms (RTT1121 also called JMF-01), which has been milled and formulated into 3 solid units of chocolate. Each chocolate contains to 10 mg of psilocybin and all three units of chocolate will be consumed concurrently during a single dosing session.

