6.7. Allowed and Prohibited Medications and Therapies

6.7.1 Prohibited Medications/Treatments

The consumption of synthetic psilocybin or psilocybin mushrooms (other than the single dose of the whole organic mushroom study drug) as well as LSD, DMT, ayahuasca, peyote, mescaline, and ketamine are forbidden during the study (and for at least 30 days prior to Study Day 1).

Medications with the potential for adverse drug-drug interactions including centrally acting serotonergic agents also are forbidden during the study.

Participants must agree not to participate in any other interventional clinical trials and/or additional treatments during this study.

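### After the single Day 1 dose, discontinuation ends only observation, yet sections 4.2, 5.3 and 7.1.8 let a consenting participant lose the Day 30 and Day 90 visits

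*Protocol*

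**What the plan says.** - **Dosing.** Section 6.5.1: "all three units of chocolate will be consumed concurrently during a single dosing session", on Study Day 1.
- **Grounds for discontinuation.** Section 4.2 lists, among other grounds: "lack of adherence to the requirements of the protocol or other issues that, in the opinion of the Investigator could confound the assessments". Safety and preliminary efficacy are the assessments meant. Section 5.3 adds as a possible reason that "they may not be able to comply with one or more eligibility criteria such as the prohibited use of certain concomitant medications". Neither section is limited to participants not yet dosed, and 7.1.8 expressly covers people who took study drug and then discontinue for whatever reason.
- **What follows.** Under 4.2 the Investigator "may ask the individual to continue to be followed for safety and indicate that they will not have to undergo any other tests" or procedures. Section 4.1 lets the EoT visit of a discontinued participant take place before Day 30. Section 7.1.8 makes it the final visit, with an exception for an ongoing adverse event.
- **Medication rules.** Section 6.7.1: "Medications with the potential for adverse drug-drug interactions including centrally acting serotonergic agents also are forbidden during the study". Exclusion 7 in section 5.1.2 concerns "the use of centrally-acting serotonergic agents within 24 hours prior to and for 72 hours following study drug administration on Study Day 1". For psychedelics and ketamine, 6.7.1 also runs through the study, while exclusion 12 requires that "the participant agrees to not use these (or similar) agents for 30 days after Study Day 1". (The synopsis numbers these exclusions 8 and 13.)
- **Analysis set.** Section 12.1 bases all analyses on everyone who received study drug.

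**The concern.** In a multi-dose trial, discontinuation for non-adherence can at least stop exposure. Here there is no exposure left to stop, so the only effect is that the trial sees less of a person who has already received the full dose. That person stays in the analysis set but has no later data.

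The primary objective is safety, and Day 90 is the scheduled visit at which late related events are sought. The late scale values are exploratory, but they are the only planned evidence on how long any change lasts. A SAP can say how to treat scores obtained after new medication. It cannot recover a visit that the protocol cancelled.

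**Working it through.** There is no figure in the plan to reproduce. The check sets the sections side by side and counts days.

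**1. Can a dosed participant be removed for medication that the eligibility criteria allow?** Take a serotonergic agent started on Day 12 (assumed day).
- Exclusion 7 ends 72 hours after dosing, at Day 4, so the start is allowed.
- The 5.3 sentence speaks of eligibility criteria, so it does not reach this case.
- Section 6.7.1, read literally, forbids the drug through Day 90: 90 − 4 = 86 days longer than exclusion 7.
- The start is therefore a breach of the protocol, and the adherence clause of 4.2 becomes available to the Investigator.

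The two serotonergic rules rest on the same rationale, interaction with the study drug, and give different end dates. The case need not be exotic. Inclusion 10 asks for no SSRI or SNRI only within 24 hours of Day 1, and inclusion 11 admits people stable on existing medication. Someone who pauses for the exclusion 7 window and resumes on Day 5 is eligible but in breach of 6.7.1.

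**2. What is lost after an early EoT?** Take an EoT on Day 12 (assumed).
- The Day 30 window opens at 30 − 5 = Day 25. The visit is 25 − 12 = 13 days before the window and 30 − 12 = 18 days before Day 30.
- From Day 12 to Day 90 is 90 − 12 = 78 days without a scheduled visit, unless an adverse event is ongoing. With an EoT on Day 8 it is 90 − 8 = 82 days.
- GAD-7, PHQ-9, BPI, NIH HEALS and C-SSRS are planned at both Day 30 and Day 90 (7.1.8, 7.1.9). Two timepoints become one, on Day 12.

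These counts can shift by a day, because Day 90 is also described as 90 days after Day 1.

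**3. What is not lost?** The early EoT collects those five scales if the participant attends. Known adverse events are followed (7.1.8, section 10), and events that change psychiatric status are collected throughout (10.3). What goes is the scheduled contact that would find new related events. Section 9.4 counts pause-rule events through Day 30 or EoT, even in discontinued participants. If that means Day 30, an early EoT leaves no scheduled contact to find them; if it means that participant's own EoT, there is no gap.

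**4. How large could it be?** The number k removed is an assumption. The bound is the exact one-sided 95% upper limit for zero late events, 1 − 0.05^(1/n), with n = 24 − k. Detection is 1 − 0.9^n, the chance of at least one event at a true rate of 10%.

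| k | Day 90 values missing (k/24) | Upper bound, 0 of n | Chance of ≥1 event |
|---|---|---|---|
| 0 | 0% | 11.7% | 92.0% |
| 1 | 4.2% | 12.2% | 91.1% |
| 2 | 8.3% | 12.7% | 90.2% |
| 3 | 12.5% | 13.3% | 89.1% |

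The loss of precision is small. These figures say nothing about bias, which would depend on why the k participants were removed.

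**The case against.** The strongest reply is that removal is discretionary and other text expects people to stay in. Inclusion 11 asks participants to report medication and psychotherapy changes during the study. Section 8.4 collects medication up to the Day 90 visit. Section 12.5 restricts the heart-rate analysis to days without medication changes, so it drops days, not people. The compliance ground in 5.3 that concerns procedures covers only those critical to assessing safety. An early EoT is permitted, not required, and a 24-hour hotline exists. All of this stands, and it shows that the route to lost visits is possible rather than certain. It does not close the route: 4.2 carries none of these limits, and 7.1.8 cancels Day 90 once it is used. The same text also shows that recording the change and keeping the participant fits the rest of the protocol.

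On medication, one can reply that exclusion 7 simply supplies the window that 6.7.1 leaves out, since section 2.3.2 describes complete excretion within 24 hours. That is a sensible reading and the one to adopt, but 6.7.1 does not say it.

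A reader might infer two stronger contradictions. The documents do not support either.
- **Day 90 after discontinuation.** Footnote 13 to Table 1 and the wearable item in 7.1.8 refer to discontinued participants who will not attend Day 90, which suggests that others might. The wording is loose, but it is conditional and fits the ongoing-event exception. It does not directly contradict the final-visit rule.
- **Psychedelics and ketamine.** Section 6.7.1 runs longer than exclusion 12, but a participant can satisfy both. An on-study rule stricter than the eligibility commitment is not a contradiction.

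**Conclusion.** The point holds as a design weakness that is cheap to repair. As written, the protocol allows scheduled Day 30 and Day 90 observation to be ended in dosed, consenting participants for reasons that no longer affect their treatment, and the serotonergic rule that can trigger this has two different end dates.

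A reader might go on to infer that participants who worsened would be removed preferentially and the results flattered. That is plausible for those who start new medication because of symptoms, but prohibited use can also be unrelated to worsening, and the document gives no basis for the size or direction of a bias. The case rests on what the text permits and on the low cost of closing it. The share of 4.2% to 12.5% missing at Day 90 assumes 1 to 3 removals among 24; the 78-day gap assumes an EoT on Day 12. The Day 90 scales are exploratory and safety is descriptive, so this should be fixed but does not undermine the trial.

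**What to change.** 1. **Sections 4.2 and 5.3.** State that once study drug has been taken, non-adherence, prohibited or new medication, or a change in psychotherapy is recorded with its date as a protocol deviation or intercurrent event and does not end follow-up. Removal for the participant's own health and withdrawal of consent remain.
2. **Section 7.1.8.** Limit the final-visit rule to participants who withdraw consent or decline further visits. Invite all other dosed participants to the scheduled Day 30 and Day 90 visits.
3. **Section 6.7.1.** State the serotonergic window of exclusion 7: 24 hours before to 72 hours after dosing. Leave the psychedelic and ketamine ban in place through Day 90 and record any breach as a deviation; shortening it would allow such use from Day 31 and contaminate the Day 90 data.

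The cost is about four sentences, with no visit or test added to the schedule. The downside is that some Day 30 and Day 90 scores will be taken on new medication. They must be flagged, because effective new treatment could itself improve them and favour the product.
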